15.1. Ethics committee and regulatory authorities

The CIP and/or other relevant documents are submitted to the appropriate EC(s). This clinical investigation will not begin until the required approval from the EC has been obtained. Any amendment to the protocol will be submitted to the same EC(s). Sponsor will notify the relevant EC(s) concerned of the end of the clinical investigation.

15.2. Data protection

As part of the investigation Coloplast A/S, [name] ("Coloplast") will collect and process the personal information the subject provides for the investigation ("subject personal data"). This includes identification and contact information (which may be anonymised depending on the nature of the investigation) as well as information about product usage experience and your health. Coloplast will comply with the EU General Data Protection Regulation (GDPR) and the Danish act on data protection ("databeskyttelsesloven"), including in connection with transfer of data to third countries, cf. chapter V of GDPR, Coloplast will only process the subjects' personal data:

- 1. To conduct the investigation and carry out related research based on subject consent (primary use), cf. articles 6(1)(a) and 9(2)(a) of GDPR,
- 2. To comply with applicable legal obligations to e.g., ensure reliability and safety, cf. article 6(1)(c) in conjunction with article 9(1)(i) of GDPR, and
- 3. If separate consent is given for secondary use of subject personal data, cf. articles 6(1)(a) and 9(2)(a) of GDPR carry out research outside the clinical protocol to improve Coloplast's products and services, and for use in education.

Part of Coloplast's processing is carried out on third-party platforms (clinical trial databases) and certain third parties are assisting Coloplast in the processing (e.g., the investigator). Such cases will imply a transfer of your personal data to the third parties, but solely for the specified purposes and with the third parties acting on instruction from Coloplast. Data may be collected and processed across the Coloplast network, which may entail processing of personal data outside the European Economic Area. In such cases, an adequate level of protection will be ensured by the third parties being subject to the standard contractual clauses on data protection adopted by the EU or to an EU-approved certification mechanism on data protection. For further information about this please the subject can always consult Coloplast's data protection officer (details below).

Subject personal data will be kept as long as required under applicable laws and regulations. The EU Medical Device Regulation obligates Coloplast to keep the data for a period of at least ten years after the investigation is completed, or, in the event that the device is subsequently placed on the market, at least ten years after the last device has been placed on the market.

If the subject has questions or queries regarding Coloplast's handling of personal information, the subject can always contact Coloplast's Data Protection Officer at [contact]. Complaints related to Coloplast's handling of subject personal information may similarly be sent to the Data Protection Officer, and the subject is also entitled to file a complaint with the relevant supervisory authority, which in the case of Denmark is the Danish Data Protection Agency (www.datatilsynet.dk).

The subject can write to [contact] at any time to request:

- Access to personal data
- Correction of errors in personal data or to erase personal data
- Limit what can be done with personal data
- To receive personal data in machine-readable format (data portability).
- Withdrawal of consents the subject has given Coloplast to process personal data

15.3. Indemnity

All subjects are fully covered by Coloplast A/S insurance throughout the investigation.

Insurance has been signed with:

XL Insurance Company SE [name] [contact]

15.4. Financial conditions

Coloplast A/S will compensate the investigator involved in the clinical investigation for his/her time and resources spent on the investigation.

The expenses include the salary to the Principal Investigator and study nurses, the cost of test products, shipments, transportation, and vouchers. All financial agreements with the investigation sites involved in the clinical investigation will be specified in the Sponsor Investigator contracts.

16. Informed consent process

Written informed consent must be obtained from all subjects participating in the investigation after thorough written and verbal information. The information is given by the Principal Investigator or his/her representative in a non-technical language. Each subject will be fully informed about the aim of the investigation, procedures, potential risks, or inconveniences and/or expected benefits, all anticipated adverse device effects and ensure ample time before deciding on participation. The subjects will be informed that their participation is voluntary and that they may leave the investigation at any time, without this having any influence on their further treatment.

The informed consent signature form includes personally dated signatures of the subject and the PI, or his/her representative. A copy will be provided to the subject.

If relevant new information is to be given during the investigation, sponsor will inform the investigators, and the new information is given to the subjects by the investigator. If new information becomes available that can significantly affect a subject's future health and medical care that information will be provided to the subject in written form. The Clinical Manager is responsible for writing the information and providing the approved Patient Information Sheet and the Consent Form to investigators that will further provide it to the subjects. If applicable, all affected subjects shall be asked to confirm their continuing informed consent in writing.

17. Subject compensation

[figure not shown]
17.1. Compensation in case of injury

Product liability and No-Fault Clinical Investigation Insurance covering the duration of the clinical investigation is in place, to enable compensation in the event of an injury to a participating subject.

17.2. Compensation for participating in the clinical investigation

Subjects are compensated for any transportation costs.

Reimbursement of transportation expenses are not taxable per local legislation. Transport expenses will be paid in appropriate portions that justify the administration throughout the investigation period.

18. Adverse events, adverse device effects and device deficiencies

18.1. Adverse events

An adverse event is any untoward medical occurrence, unintended disease or injury, or untoward clinical signs (including abnormal laboratory findings) in subjects, whether related to the investigational medical device(s) or the comparator(s), or the procedures involved. The adverse event shall be marked with the intensity mild, moderate, or severe. This could include events such as headache or dizziness.

18.2. Adverse device effect

An adverse event, which is related to the use of the investigational medical product, is an adverse device effect, and should be marked as related or possibly related with causal relationship on the adverse event form.

The definition of an adverse device effect includes any event resulting from insufficiencies or inadequacies in the instruction for use, or any malfunction of the medical device, as well as any event resulting from use error or from intentional misuse of the device.

Table 5 lists anticipated adverse device effects that may occur, based on the IFU and their likely incidence rates based on adverse events reported in clinical studies (17).

Table 5: Anticipated adverse device effects and their likely incidence rates

ANTICIPATED ADE	INCIDENCE RATE		
Skin irritation/inflammation/itching	0.13 %		
Maceration	0.09 %		
Pain	0.09 %		
Hyper granulation	0 %		
Blistering	0 %		
Allergic skin reaction	0.09 %		

Temporary skin irritation upon removal of the dressing is not considered an adverse device effect, however an abnormal development in intensity or duration should be considered as such.

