Clinical Investigation Plan

CP351 - BISIL

Biatain® Silicone 3D fit

[figure not shown]
A randomised controlled investigation comparing the clinical performance and cost effectiveness of Biatain® Silicone with standard of care dressing including filler in chronic wounds

January 2023 - January 2024

IRAS ID: 315855

Last submission date: March 15, 2023

CHANGE LOG

This confidential document is the property of Coloplast A/S. No unpublished information contained herein may be disclosed without written approval of Coloplast A/S.

SYNOPSIS OF THE CLINICAL INVESTIGATION

Title and aim

A randomised controlled investigation comparing the clinical performance and cost effectiveness of Biatain® Silicone with standard of care dressing including filler in chronic wounds.

The overall aim of this investigation is to evaluate the clinical performance and cost-effectiveness of Biatain® Silicone compared to standard of care (SoC) defined as Mepilex® Border and AQUACEL® EXTRA™ Hydrofiber® Dressing in the treatment of chronic wounds with wound depth down to 20 mm.

Investigational test product and comparator

The investigational test product is Biatain® Silicone. Biatain® Silicone is intended to be used for moist wound healing and exudate management.

The comparator products are Mepilex® Border and AQUACEL® EXTRA™ Hydrofiber® Dressing.

Intended use and purpose

All products, investigational test products as well as comparator products, are CE-marked and will be used within the intended purpose, indications and user population.

Objectives

The primary objective is to demonstrate that the clinical performance of Biatain® Silicone is comparable to standard of care (Mepilex® Border and AQUACEL® EXTRA™ Hydrofiber® Dressing).

The secondary objective is to evaluate the cost-effectiveness of Biatain® Silicone compared with standard of care (Mepilex® Border and AQUACEL® EXTRA™ Hydrofiber® Dressing).

Design of the investigation

The clinical investigation is a two-arms, open-labelled, stratified, randomized, controlled, multicentre investigation.

The cohort will in total consist of 100 subjects with chronic wounds with wound depth down to 20 mm. The subjects will be included and randomised to one of two groups receiving either Biatain® Silicone or Mepilex® Border and AQUACEL® EXTRA™ Hydrofiber® Dressing at >12 sites across the UK.

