4.8. Description of the comparator products

Mepilex® Border is a CE-marked soft silicone full-adhesive wound care dressing intended for moist wound healing (Figure 2). The dressing is produced and marketed by Mölnlycke Health Care. Mepilex® Border is a five-layer bordered foam dressing, indicated for the management of a wide range of exudating wounds, such as leg and foot ulcers, pressure ulcers, surgical and traumatic wounds. See IFU in Appendix 2.

Mepilex® Border will be available in the following sizes in this investigation:

- 7 cm x 7.5 cm
- 10 cm x 10.5 cm
- 15 cm x 17.5 cm
- Heel 22 cm x 23 cm

Figure 2: Investigational comparator product, Mepilex® Border

AQUACEL® EXTRA™ Hydrofiber® Dressing is a CE-marked sterile, white, fibrous dressing derived from 100% sodium carboxymethylcellulose. It is a versatile, primary dressing indicated for use on moderately and highly exuding chronic and acute wounds. The dressing is produced and marketed by ConvaTec. The indication for using AQUACEL® EXTRA™ Hydrofiber® Dressing is for the management of leg ulcers, pressure ulcers, diabetic ulcers, surgical wounds, traumatic wounds and for exudate absorption. Please refer to the IFU in Appendix 3.

AQUACEL® EXTRA™ Hydrofiber® Dressing will be available in the following sizes in this investigation:

- 5 cm x 5 cm
- 10 cm x 10 cm

The investigational comparator products will be used according to intended use and indications during the investigation.

5. Design of the clinical investigation

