Monitor will align with data management in each investigation, how data management will be informed about all deviations.

The following information about the deviation will be collected:

- Site ID, Subject ID
- Deviation Date and Investigation Visit
- Date deviation was discovered
- Clear and concise description of the event
- Does the deviation affect the safety of the subject?

Corrective action taken, including the date of the corrective action. Please note corrective
action can be site was re-educated on a procedure. Ensure the corrective action is
documented.

14. Device Accountability

All access to the investigational devices, including comparators, used in the clinical investigation is controlled by storage procedures and device accountability logs as described below. The investigational devices must only be used in this clinical investigation and only according to the CIP.

Sponsor keeps a device accountability log that states the physical location of all investigational devices from shipment of investigations devices to the investigational sites until return or disposal.

The PI, or delegate, keeps records documenting the receipt, use and return and disposal of the investigational devices, which includes:

- Name of the product received
- Date of receipt.
- Identification of each investigational device (batch no./lot no)
- The expiry dates.
- Number of products received
- Number of products distributed to subjects
- The date(s) of use.
- Subject identification.
- The date on which the investigational device was returned/explanted from the subject.
- The date of return unused, expired or malfunctioning investigational products was returned to Sponsor, if applicable

15. Statement of compliance

The clinical investigation is conducted in accordance with:

- Ethical principles that have their origin in the Declaration of Helsinki, 1964, Last amended at the 59th WMA General Assembly, Brazil, October 2013.
- MDD 93/42/EEC as amended by Directive 2007/47/EC (commonly known as the Medical Device Directive).
- MDR (EU) 2017/745
- ISO 14155:2020 "Clinical Investigation of medical devices for human subjects Good clinical practices".
- The EU General Data Protection Regulation (2016/679)
- Any applicable regional or national regulations will be specified in the country specific CIP.

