18.3. Device deficiency

A device deficiency is the inadequacy of the investigational medical device or comparator with respect to its identity, quality, durability, reliability, usability, safety, or performance. This includes malfunctions, use errors and inadequacy in the information supplied by the manufacturer including labelling.

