18.7. Investigator's reporting responsibilities

PI at each site must assess all (S)AE's that occur at his/her site.

- All serious adverse events and serious adverse device effects must be reported to sponsor within 24 hours of the site becoming aware of the event.
- A device deficiency that could have led to a serious adverse event but did not because suitable
 action was taken, intervention had been made or because of fortunate circumstances should
 be reported to sponsor within 24 hours of the site becoming aware of the event.
- New findings and/or updates in relation to already reported serious events should also be reported to sponsor within 24 hours of the site becoming aware of the event.
- Device deficiencies and all adverse device effects related to CE marked Coloplast investigational product and/or comparator must be reported to sponsor within 24 hours of becoming aware of the event.

When reporting the SAE, the relationship to the test material shall be described whether the event is considered:

- Not related, the event has no temporal relationship with the use of the test material or the
- procedures.
- Unlikely related, the relationship with the use of the test material seems not relevant and/or
 the event can be reasonably explained by another cause, but additional information may be
 obtained.
- Possible related, the relationship with the use of the test material is weak but cannot be ruled
 out completely. Alternative causes are also possible (e.g., an underlying or concurrent illness/
 clinical condition or/and an effect of another device, drug, or treatment). Cases where
 relatedness cannot be assessed, or no information has been obtained should also be
 classified as possible.
- Probably related, the relationship with the use of the test material seems relevant and/or the
 event cannot reasonably be explained by another cause, but additional information may be
 obtained.
- **Definitely related/Causal relationship,** the event has a temporal relationship with the test material use/application or procedures.

The investigator will assess intensity for each AE and SAE reported during the investigation and assign it to one of the following categories:

- Mild, the intensity of the event is mild with no further action or intervention
- Moderate, the intensity of the event will lead to an action or intervention to solve the event

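### Section 18.2 ties an adverse device effect to the investigational product only, while section 18.7 expects such effects for the comparator too, so the same event may be classified differently by arm

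*Combined protocol and SAP*

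**What the plan says.** Section 18.2 of the protocol reads "An adverse event, which is related to the use of the investigational medical product, is an adverse device effect". The comparator is not mentioned. It is mentioned in the definitions on either side: an adverse event under 18.1 counts "whether related to the investigational medical device(s) or the comparator(s), or the procedures involved", and a device deficiency under 18.3 is the "inadequacy of the investigational medical device or comparator with respect to its identity", quality and further properties. Section 18.4.1 builds the serious adverse device effect (SADE) on the adverse device effect (ADE), and 18.4.3 builds the unanticipated form on the SADE. Both inherit whatever 18.2 leaves out.

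Section 18.7 adds two rules. The first is a 24-hour duty: "Device deficiencies and all adverse device effects related to CE marked Coloplast investigational product and/or comparator must be reported to sponsor". The second concerns causality of serious adverse events (SAEs): "When reporting the SAE, the relationship to the test material shall be described whether the event is considered", followed by five categories worded around the same term. The plan does not define *test material*. The nearest defined term is in the synopsis: "The investigational test product is Biatain® Silicone", with Mepilex Border and AQUACEL Extra listed separately as comparators.

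For the analysis, section 10.1 plans only to list adverse events and to summarise them where that is useful. It specifies no comparison of ADEs between arms.

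**The concern.** In a randomised comparison, relatedness to the study dressing should be judged by the same rule in both arms. If 18.2 is read with the synopsis, maceration attributed to Biatain Silicone is an ADE, while the same maceration attributed to a comparator dressing is only an adverse event. For an SAE in the comparator arm, the investigator is not told which device to rate it against.

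The trial is open-label and runs at more than 12 sites, so each classification is made with the allocation known, and sites may resolve the ambiguity in different ways. At stake are the by-arm counts of ADEs, SADEs and related SAEs. There is also a consequence for conduct: SAEs go to the sponsor within 24 hours in any case, but for a non-serious event the ADE label decides whether that deadline applies.

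**Working it through.** The plan states no figure on this point, so the check is a side-by-side reading followed by a rough scale.

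**1. Where the comparator is covered**

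| Place | Term used | Comparator covered? |
|---|---|---|
| 18.1, adverse event | investigational device(s) or comparator(s) | yes, named |
| 18.2, ADE | investigational medical product | not named |
| 18.3, device deficiency | investigational device or comparator | yes, named |
| 18.4.1, SADE | built on ADE | as 18.2 |
| 18.4.3, forwarding to Vigilance | investigational test product, with Biatain Silicone named | no, expressly |
| 18.7, 24-hour duty | investigational product and/or comparator | yes, named |
| 18.7, SAE causality | test material | undefined |

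Within section 18, *investigational* is set against *comparator* in 18.1, 18.3 and the 18.7 duty. A reader who carries that contrast into 18.2 concludes that comparator effects are outside the definition. The 18.7 duty then asks for reports of a class of event that the definition omits.

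**2. What *investigational* means elsewhere**

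- Synopsis: the test product is Biatain Silicone only.
- Section 14: "All access to the investigational devices, including comparators, used in the clinical investigation is controlled by storage procedures", so comparators are included.
- Section 4.8: "Figure 2: Investigational comparator product, Mepilex® Border".
- Section 10.1, per-protocol set: subjects must not have used dressings other than the investigational test product(s). This has to include the comparators, or the whole standard-of-care arm would drop out.

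The word therefore has two meanings in one document, and 18.2 does not say which applies.

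**3. Scale**

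Table 5 gives rates for anticipated ADEs. Their sum is 0.13 + 0.09 + 0.09 + 0 + 0 + 0.09 = 0.40%. The denominator is not stated, so both cases are shown. Assumptions: the rates add, the same rates apply in either arm, and units are independent. The number per arm is 40 (completers, section 10.2) to 50 (100 / 2, assuming 1:1 allocation). Expected count = n × 0.004; P(at least one) = 1 − (1 − 0.004)^n.

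| Assumed denominator | n per arm | Expected ADEs | P(at least one) |
|---|---|---|---|
| per subject | 40 | 0.16 | 14.8% |
| per subject | 50 | 0.20 | 18.2% |
| per dressing, 12 per subject (the maximum in 4.7) | 480 | 1.92 | 85.4% |
| per dressing, 12 per subject | 600 | 2.40 | 91.0% |

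In all four cases the expected count is below three per arm. With counts this small, one or two comparator events classified differently would change the descriptive table.

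**The case against.** The strongest reply is that the plan, read as a whole, does include comparator effects. The 24-hour duty in 18.7 names them, sections 14 and 4.8 use *investigational* for the comparators, and the per-protocol criterion only works on the wide reading. Where the sponsor means Biatain Silicone alone, as in the Vigilance sentence of 18.4.3, it says so. The *test material* scale is introduced for SAEs; for ADEs in general, 18.2 has the event marked related or possibly related on the adverse event form. That form is not in the documents, so it cannot be said to lack a field for the dressing. No by-arm ADE analysis is pre-specified.

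Most of this stands, and it rules out a stronger inference that a reader might draw: that the comparator arm can have no device effects at all, and that safety in the two arms cannot be compared. The 18.7 duty contradicts the first part. The second fails because adverse events and device deficiencies are defined for both arms.

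The reply does not remove the contradiction. A reporting duty does not amend a definition, and two meanings of one word are the reason sites may diverge. Nor does the lack of a planned test remove the interest in the counts, since section 20 requires the report to evaluate critically all data collected.

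**Conclusion.** Wrong as written, as an internal contradiction in a safety definition; minor severity. Section 18.2 leaves comparator-related events out of the ADE definition, 18.7 requires them to be reported as ADEs, and the SAE causality scale refers to an undefined term. Descriptive counts of ADEs, SADEs and related SAEs by arm are therefore unreliable. All-cause adverse events, device deficiencies, and the primary and secondary endpoints are unaffected.

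The documents do not fix the number of events affected. The range of 0.16 to 2.40 expected ADEs per arm rests on the assumptions stated with the calculation. If every site took the narrow reading, the distortion would run against Biatain Silicone. If sites differ, its direction is unknown.

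**What to change.** - In 18.2, define an ADE as an adverse event related to the use of the investigational device or of either comparator dressing. The SADE definition then follows without further change.
- In 18.7, replace *test material*, or define it, as the allocated study dressing(s) in both arms: Biatain Silicone, or Mepilex Border and AQUACEL Extra.
- Record on the adverse event form which dressing is implicated, if the form does not already do so.
- In 10.1, state that ADEs and SADEs are listed or summarised by arm on this single definition.

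The cost is a few wording changes and at most one form field. No added visits or subjects are needed, and 18.7 already asks sites to report comparator-related effects. Events recorded before the change should be checked against the new definition before database lock.
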